14.2. Sample Size Justification

This study was designed and powered to show non-inferiority between the Test lens compared to the Control lens with respect to CLUE comfort and vision. It was assumed there was no difference between the Test and Control lenses. The sample size was calculated to achieve a minimum statistical power of 90% and a type I error of 5%.

The sample size calculation was based on historical data from a similar study, CR-5960 The Test lens from CR-5960 is the Control for this study. CR-5960 enrolled 133 subjects, of which 130 (97.7%) were dispensed study lenses. Of the dispensed subjects, 127 (95.5%) completed the study and 3 (2.3%) subjects were discontinued. The per-protocol population included 121 (91.0%) subjects out of the total 127 that completed. Table 4 summarizes CLUE scores from CR-5960 at the 2-week follow-up.¹³

Table 4: Descriptive CLUE scores from CR-5960 (Historical Data)

| CLUE Domain | Study Lenses | |
|-----------------------------------|------------------|---------------------------|
| | Acuvue Oasys | Solace – 25% differential |
| Comfort [mean (SD ¹)] | 61.185 (24.2024) | 64.339 (24.2132) |
| Vision [mean (SD ¹)] | 66.792 (20.0073) | 69.445 (20.1752) |

¹SD: Standard Deviation

Sample size calculation for CLUE comfort and vision were carried out using an approximation of the power of an F-test derived from the non-centrality parameter calculated form the observed F-statistic of a linear model. ¹⁴

Model details:

CLUE comfort and vision were analyzed separately using a linear mixed model. Lens type, was included as the only fixed effect. A compound symmetric (CS) covariance was used to model the correlation between measurements within the same subject across study periods. Below is the variance-covariance matrix used in the CLUE each model.

$$\sum_{comfort} \begin{pmatrix} 349.3 & 110.9 & 110.9 \\ 110.9 & 349.3 & 110.9 \\ 110.9 & 110.9 & 349.3 \end{pmatrix}$$

$$\sum_{vision} \begin{pmatrix} 257.4 & 82.1 & 82.1 \\ 82.1 & 257.4 & 82.1 \\ 82.1 & 82.1 & 257.4 \end{pmatrix}$$

Table 5: Sample Size Calculations for CLUE Comfort and Vision

| CLUE Domain | Number to Complete | Power (%) |
|--------------------|--------------------|-----------|
| Comfort | 50 | 77% |
| | 60 | 85% |
| | 80 | 93% |
| Vision | 50 | 88% |
| | 60 | 93% |
| | 80 | 98% |

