Assuming no difference between the Test lens and Control lens, the sample size required to achieve non-inferiority with a minimum power of 90% and a type I error controlled at 5% was estimated to be 80 subjects.

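### Table 5's power at 80 completers (93% comfort, 98% vision) does not follow from the printed covariance matrices, which as labelled give 65–67% and 78–80%; their diagonals also fall well below the Table 4 variances

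*Combined protocol and SAP*

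**What the plan says.** Section 14.2 bases the sample size on historical data from CR-5960 and on a linear mixed model with compound symmetry across the three periods. Of that model it says "Lens type, was included as the only fixed effect". It introduces the two matrices with "Below is the variance-covariance matrix used in the CLUE each model". The first row for comfort is "349.3 & 110.9 & 110.9" and for vision "257.4 & 82.1 & 82.1".

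Table 4 gives the CR-5960 standard deviations at two weeks: 24.2024 and 24.2132 for comfort, 20.0073 and 20.1752 for vision.

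Table 5, headed "Number to Complete | Power", lists power at 50, 60 and 80 as 77%, 85% and 93% for comfort and 88%, 93% and 98% for vision. Section 14.2 concludes that the number needed "with a minimum power of 90% and a type I error controlled at 5% was estimated to be 80 subjects". The Synopsis and Sections 3.1, 4.1 and 4.3 all treat 80 as the total number of completers in the study.

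**The concern.** The matrices, the margin, the assumed difference of zero, the design and the decision rule are all printed, so Table 5 should be reproducible from them. It is not.

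The target of 80 rests on a minimum power of 90%. If the matrices are right as labelled, two equal lenses would miss non-inferiority on comfort about one time in three. Section 2.3 requires both endpoints to succeed, so the chance of overall success could be no higher than the comfort figure. If instead the matrices are mislabelled, the target may be sound and only the text needs correcting. A reader cannot tell which case holds.

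The matrices also do not match the historical standard deviations printed just above them, so the source of the inputs cannot be traced.

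**Working it through.** **Inputs.** Margin −5 (Section 2.3). True difference 0 (14.2). Non-inferiority if the lower limit of a two-sided 95% interval is above −5, i.e. one-sided 2.5% (14.5). Sequences Test/Control/Control and Control/Test/Test, in blocks of 2 (5.1), so N/2 per sequence. Matrices from 14.2.

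**Within-subject variance, as labelled** (diagonal minus off-diagonal):
- Comfort: 349.3 − 110.9 = 238.4
- Vision: 257.4 − 82.1 = 175.3

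**Standard error of the lens difference.**
- Section 14.5 fixed effects (sequence, period, lens, carryover): SE = √(1.5 σ²w / N), df = 2N − 4. At N = 80: comfort √(1.5 × 238.4 / 80) = 2.114; vision √(1.5 × 175.3 / 80) = 1.813.
- Lens only, as 14.2 describes, with c the covariance: 1/SE² = (2N/3)/σ²w + (N/12)/(σ²w + 3c), df = 2N − 1. At N = 80, comfort: 53.33/238.4 + 6.667/571.1 = 0.2354, SE = 2.061. Vision: 53.33/175.3 + 6.667/421.6 = 0.3201, SE = 1.768.

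**Power** comes from the noncentral t with shift 5/SE. For comfort with the 14.5 effects the shift is 5/2.114 = 2.365 against a critical value of 1.975, which gives 65.2%.

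| Reading | Comfort at 50 / 60 / 80 | Vision at 50 / 60 / 80 |
|---|---|---|
| Table 5 | 77 / 85 / 93 | 88 / 93 / 98 |
| As labelled, N total, lens only | 47.6 / 54.9 / 67.4 | 60.0 / 68.1 / 80.3 |
| As labelled, N total, 14.5 effects | 45.7 / 52.9 / 65.2 | 57.9 / 65.9 / 78.3 |
| As labelled, N per sequence, lens only | 77.0 / 84.1 / 92.8 | 88.2 / 93.2 / 97.9 |
| As labelled, N per sequence, 14.5 effects | 74.9 / 82.2 / 91.5 | 86.6 / 92.0 / 97.3 |
| 110.9 and 82.1 as residual variances, N total, 14.5 effects | 77.4 / 84.6 / 93.1 | 88.4 / 93.3 / 98.0 |
| 110.9 and 82.1 as residual variances, N total, lens only | 78.1 / 85.2 / 93.5 | 88.9 / 93.7 / 98.1 |

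**Other ways to close the gap.** Section 14.2 does not state whether its 5% is one- or two-sided. A one-sided 5% test at 80 total gives 76.1–78.0% for comfort and 86.5–87.9% for vision, still short. Nor does the baseline covariate of 14.5 rescue it: even if it removed all between-subject variance and left the within-subject variance unchanged, power at 80 would be about 71% and 83% (normal approximation, lens only).

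**Total completers for 90% power.**
- As labelled: comfort 144 (lens only) or 152 (14.5 effects); vision 108 or 112.
- 110.9 and 82.1 as residual variances, 14.5 effects: 72 and 54.
- Conversely, 90% power at 80 total needs a within-subject variance of at most about 125 (14.5 effects) or 130 (lens only).

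**Table 4 against the diagonals.**
- Comfort: (24.2024² + 24.2132²)/2 = 586.0; 349.3/586.0 = 0.596, i.e. 40% lower.
- Vision: (20.0073² + 20.1752²)/2 = 403.7; 257.4/403.7 = 0.638, i.e. 36% lower.

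If the missing variance is assumed to lie between subjects, power at 80 as labelled is 65.2% and 78.3% (14.5 effects) or 66.2% and 79.3% (lens only), almost unchanged.

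**The case against.** The best defence is that the matrices are merely mislabelled. With 110.9 and 82.1 as residual variances and the Section 14.5 fixed effects, all six Table 5 entries come out exactly after rounding. That reading contradicts only the label, whereas counting N per sequence contradicts every statement that 80 is the study total. On this view Table 5 is right, 80 is adequate, and the figures of 65–67% or 144–152 completers describe a reading that reproduces no cell of the table.

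This has real force, and it is why the point does not say that the trial is underpowered. It does not settle the matter. Section 14.2 names a lens-only model for the calculation, and under that model neither alternative matches every cell: the residual reading gives 78.1% for comfort at 50 against 77%, and the per-sequence reading gives 84.1% at 60 against 85%. Either way, something printed in Section 14.2 is wrong.

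On Table 4, it can be said that the table is descriptive, that its analysis set is not stated, and that linking text or reference 13 may have been removed from the public copy. That is fair. Baseline adjustment, a random effect outside the printed matrix, or another data source could each explain the gap, although adjustment would conflict with lens type being the only fixed effect. The gap is a question about the origin of the inputs and does not itself show lower power.

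**Conclusion.** The concern holds. With the matrices as labelled and 80 completers in total, power is 65.2–67.4% for comfort against 93% stated, and 78.3–80.3% for vision against 98%. These figures assume a true difference of 0, the margin of 5, equal sequences and the two-sided 95% interval. No reading tried that keeps both the matrix labels and 80 as the total reaches the Table 5 figures.

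Whether 80 is enough depends on an answer that the documents do not give. It is enough if 110.9 and 82.1 are residual variances. It falls well short of 90% on both endpoints if the matrices are right as labelled. The difference between the diagonals and Table 4 (40% and 36%) is arithmetically certain but secondary, and the removed text may account for it; it does not affect the mismatch between the matrices and Table 5, whose inputs are all printed.

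**What to change.** In Section 14.2:

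1. State which data and which fitted model produced the matrices, and what each entry is: total variance, covariance or residual variance.
2. If the fit was adjusted, correct the sentence on fixed effects and explain why the diagonals are below Table 4.
3. State whether the Table 5 sample sizes are total or per sequence.
4. Restate Table 5 and the 90% claim for 80 total completers.

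If the within-subject variance for either endpoint is above about 125, the 90% claim or the target of 80 has to change. The Table 4 variances should not simply be substituted: Table 4 gives no covariance and so does not determine crossover power.

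The cost is a clarification and a recalculated table, from data the sponsor already holds. Only if the matrices are right as labelled is there a larger cost: a lower stated power, or 144–152 completers for comfort.

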14.3. Analysis Populations

Safety Population:

All subjects who were administered any test article excluding subjects who drop out prior to administering any test article. At least one observation should be recorded.

Per-Protocol Population:

All subjects who have successfully completed all visits and did not substantially deviate from the protocol as determined by the trial cohort review committee prior to database hard lock (Per-Protocol Population). Justification of excluding subjects with protocol deviations in the per-protocol population set will be documented in a memo to file.

Intent-to-Treat (ITT) Population:

All randomized subjects regardless of actual treatment and subsequent withdrawal from study or deviation from protocol. At least one observation should be recorded.

14.4. Level of Statistical Significance

All planned analysis for this study will be conducted with an overall type I error rate of 5%.

14.5. Primary Analysis

CLUE Comfort and Vision

Overall comfort and vision CLUE scores will be analyzed separately using a linear mixed model adjusting for baseline values as a covariate. Sequence of lens wear, period, lens type, first order carryover effect will be included in each model as fixed effects. An appropriate covariance structure will be used to model the residual errors between measurements within same subject across study periods (R-side). The covariance structure will be selected based on the finite-sample corrected Akaike's Information Criterion. Covariance structures considered include:

- Unstructured Covariance Structure (UN)
- Homogenous Compound symmetry (CS)
- Heterogeneous Compound Symmetry (CSH)
- Autoregressive first order (AR (1))

For autoregressive first order (AR (1)), Site and Subject nest within site will be included as random effects (G-side). For the remaining covariance structures only site will be included as a random effect (G-side). The Kenward and Roger method (Kenward and Roger, 1997) will be used for the denominator degree of freedom.

Comparisons between the test and control lens at the 2-weeks follow-up will be carried out using two-sided 95% confidence intervals constructed for least-square mean differences (test

minus control). The lower limit of the 95% confidence interval will be compared to -5 and 0 to test for non-inferiority and superiority, respectively. Non-inferiority of the test lens relative to the control will be concluded if a lower limit is above -5. If non-inferiority is established the superiority will be tested. Superiority will be declared if the lower limit of the 95% confidence interval is above 0.

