4. STUDY DESIGN AND RATIONALE

4.1. Description of Study Design

This study is a randomized, 4-visit, double-masked, 2x3 bilateral crossover, dispensing trial. Approximately 90 subjects will be screened and enrolled to ensure that at least 80 subjects to complete.

The study begins with an initial visit (Visit 1). If a subject is found to meet all eligibility criteria, they will be random to one of two lens wear sequences (Test/Control/Control or Control/Test/Test).

If the subject is dispensed study lenses at the initial visit, 3 follow-up visits will be conducted. The follow-up visits occur approximately 2, 4 and 6 weeks after the initial visit. Unscheduled follow-up visits may occur during the study. Subjects will be advised to wear the study lenses at least five (5) days per week for at least six (6) hours per day for a period of two weeks each. Lens replacement is scheduled at 2 and 4-week follow-up visits.

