5. TEST ARTICLE ALLOCATION AND MASKING

5.1. Test Article Allocation

Use of the test articles will be randomized using a randomization scheme supplied by the study biostatistician.

This is a multi-site, double-masked, dispensing and randomized study. The study lenses will be worn in a bilateral and random fashion using a 2 treatment by 3 period (2x3) crossover design.

A block size of two (2) sequences will be utilized. A computer-generated randomization scheme will be used to randomly assign subjects, in blocks of 2, to one of the two possible lens wear sequences (TEST/CONTROL/CONTROL or CONTROL/TEST/TEST). The random scheme will be generated by site using the PROC PLAN procedure from SAS Software Version 9.4 or higher (SAS Institute, Cary, NC).

The study site must follow the randomization scheme provided and complete enrollment according to the randomization list and not pre-select or assign subjects. The randomized

assignment of subjects will be performed at the first visit prior to the first fitting. The following must have occurred prior to randomization:

- Informed consent has been obtained
- Subject meets all the inclusion / exclusion criteria
- Subject history and baseline information has been collected.

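### Section 14.5 lets AICc choose the covariance, which in this design sets essentially only the standard error behind the -5 test; pre-specifying unstructured would be safer at almost no cost

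*Combined protocol and SAP*

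**What the plan says.** Section 5.1 uses a computer-generated scheme to "randomly assign subjects, in blocks of 2, to one of the two possible lens wear sequences": Test/Control/Control (TCC) or Control/Test/Test (CTT). Periods 2 and 3 are thus the same lens for every subject.

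Under Section 14.5, CLUE comfort and vision are "analyzed separately using a linear mixed model adjusting for baseline values as a covariate". On the fixed part it says: "Sequence of lens wear, period, lens type, first order carryover effect will be included in each model as fixed effects". The candidate structures are unstructured (UN), compound symmetry (CS), heterogeneous compound symmetry (CSH) and AR(1), the last with a random subject effect added. On the choice among them: "The covariance structure will be selected based on the finite-sample corrected Akaike's Information Criterion". Degrees of freedom follow Kenward-Roger. Non-inferiority is concluded if the lower two-sided 95% limit for Test minus Control is above -5, and Section 2.3 requires this for both endpoints. Section 14.7 applies the same analysis to CLUE handling.

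For the sample size, Section 14.2 states: "A compound symmetric (CS) covariance was used to model the correlation between measurements within the same subject across study periods". It gives no separate correlation for two periods on the same lens.

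**The concern.** Choosing a covariance from the data is usually defended because it weights the observations better. That benefit is absent here if the fixed effects already use up all six sequence-by-period means. The choice then affects only the standard error and its degrees of freedom.

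A lasting individual liking or dislike of one lens makes a subject's period 2 and 3 scores more alike than either is to period 1. CS, CSH and AR(1) plus subject cannot represent that pattern; UN can. Kenward-Roger is model-based and does not repair a wrong structure. A standard error that is too small raises the lower limit, so a lens truly 5 points worse would pass more often than the nominal 2.5%.

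**Working it through.** **1. The estimate.** Let p_k be the TCC mean minus the CTT mean in period k, δ the sequence difference, τ the lens effect (Test minus Control) and λ the carryover difference.

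- E(p1) = δ + τ
- E(p2) = δ - τ + λ
- E(p3) = δ - τ - λ

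Hence (2·p1 - p2 - p3)/4 estimates τ. The fixed part (intercept 1, sequence 1, period 2, lens 1, carryover 1) has rank 6 for six means, so this is the only unbiased estimate built from them, whatever the covariance. The weights (0.5, -0.25, -0.25) sum to zero, so a common baseline slope and a site intercept cancel. Numerically, generalised least squares with baseline and random site gave the same estimate to 6 decimals under CS, AR(1)-type and two unstructured matrices with complete data. With 10 of 90 subjects incomplete it moved by up to 0.16 points (SD about 0.05-0.06). That check took the Section 14.2 matrices literally, where the standard error is near 2.1.

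**2. Reproducing Table 5.** Taken literally (variance 349.3, covariance 110.9), 80 subjects in total give 65% power for comfort and 78% for vision with the full Section 14.5 model. Reading 349.3 and 257.4 as subject variances and 110.9 and 82.1 as residual variances reproduces the table:

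- Comfort, N = 80: variance = (6 × 110.9/16) × (1/40 + 1/40) = 2.079, so SE = 1.442 and power is 93.1% (Table 5: 93%).
- N = 50/60/80: comfort 77.4/84.6/93.1% (Table 5: 77/85/93); vision 88.4/93.3/98.0% (Table 5: 88/93/98).

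I use this reading below. The relative understatement in step 3 depends only on the share f, not on the reading.

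**3. The standard error.** Take equal period variances v, different-lens covariance s and same-lens covariance s + g. For the contrast c = (2, -1, -1)/4:

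- True: 16·c'Σc = 6v - 6s + 2g
- CS, which averages the covariances to s + g/3: 6v - 6s - 2g
- AR(1) plus subject: about 6v - 6s - g

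With v - s = 110.9, g = f × 110.9 and 80 completers:

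| Share f | SD of a subject's true lens difference, √(2g) | True SE | CS SE | CS error | AR(1)+subject error |
|---|---|---|---|---|---|
| 10% | 4.7 | 1.466 | 1.418 | -3.3% | about -2.4% |
| 20% | 6.7 | 1.489 | 1.393 | -6.5% | about -4.8% |
| 30% | 8.2 | 1.512 | 1.368 | -9.5% | about -7.1% |

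The share f is an assumption. At f = 20% with CS chosen, the limit moves by 1.975 × (1.489 - 1.393) = 0.19 points.

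CSH also understates. On the literal matrices, with same-lens correlation exceeding different-lens correlation by 0.1 to 0.4, the understatement is 4.6-15.2% for CS, 4.2-13.8% for CSH and 3.4-11.2% for AR(1) plus subject.

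**4. After AICc selection.** Simulation of 120,000 trials per setting, 80 completers, true difference -5, REML fits of all four structures, site and dropout ignored:

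| Share f | UN chosen | False non-inferiority under the AICc rule |
|---|---|---|
| 0% | - | 2.4% |
| 10% | - | 2.7% |
| 20% | 13% | 3.0% |
| 25% | 21% | 3.1% |
| 30% | 31% | 3.1% |
| 50% | - | 2.7% |

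At 20-30%, fixing UN gives 2.5-2.6% and fixing CS 3.3-3.8%. Repeat runs of 40,000 trials gave 2.98, 3.04 and 3.10% at 20, 25 and 30% under AICc, with 2.4-2.5% for UN.

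**5. Exceptions.** With period SDs in ratio 1 : 1.3 : 1.3 and correlations 0.317 (different lens) and 0.417 (same lens), CS overstates the SE by about 1.9%. If likeness is purely serial (ρ12 = ρ23 > ρ13), AR(1) plus subject is correct, while CS understates by about 5%.

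**The case against.** The plan already has what is normally asked for: a closed list that includes UN, an objective criterion and a stated degrees-of-freedom method. Nothing is left to the analyst's discretion. That stands, so this is no charge of an open-ended analysis.

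The size is small and its driver is unsupported. A share of 20-30% means individual true lens differences with an SD of 6.7-8.2 points, wider than the margin itself. In the visible rows of Table 1 the two lenses differ only in cure technique; both contain the same UV-blocker and are masked. Even 10% (SD 4.7) may be generous. Because both endpoints must pass, the study-level error cannot exceed the per-endpoint rate. All of this stands and sets the priority.

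A reader might also infer more than the documents support:

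- **That selection can never alter the estimate.** This is exact only with complete data. About 90 are enrolled for 80 completers, the ITT set keeps withdrawals, values are not imputed, and Section 14.5 names no primary population.
- **That every structure but UN always understates the error.** This needs similar period variances and a same-lens correlation above both different-lens correlations; step 5 shows the exceptions.
- **That AICc usually rejects UN.** This holds for smaller interactions only. On the literal matrices, UN was chosen in 59% and 87% of runs at correlation excesses of 0.3 and 0.4.
- **That the 3.3-3.8% for fixed CS describes the plan.** It does not, because Section 14.5 does not fix CS.

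**Conclusion.** The point holds in a limited form. With complete data, AICc selection sets only the standard error and degrees of freedom of the limit compared with -5; with the planned dropout this is very nearly so. Under a subject-by-lens effect with similar period variances, three of the four candidates understate that standard error. AICc often fails to choose UN when the effect is moderate.

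For subject-by-lens shares of 10-30%, false non-inferiority per endpoint is about 2.7-3.1%, against about 2.5% with UN fixed. The lower end is the more plausible. These figures rest on 80 complete subjects, the variance reading that reproduces Table 5, and an assumed share. They do not show that the planned analysis is seriously anti-conservative. This is a cheap improvement of low priority.

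**What to change.** In Section 14.5, and for handling through Section 14.7, replace AICc selection with a pre-specified unstructured covariance and Kenward-Roger degrees of freedom.

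Name a fallback for non-convergence that keeps subjects with incomplete periods, for example CS with an empirical sandwich standard error and a small-sample correction, and state its degrees-of-freedom rule. The two-sample t interval on each subject's (2·y1 - y2 - y3)/4 drops anyone missing a period, so give it only as a completer check.

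The cost is wording, plus about 78 instead of 156 denominator degrees of freedom. If compound symmetry is exactly true, the critical value rises from 1.975 to 1.991 (1.991/1.975 = 1.008, an interval under 1% wider) and comfort power falls from 93.1% to 92.9%.
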